In the second part of the interview, we will show the the interviewee our plans (below) for a treatment app, using item lists, onscreen mockups, and/or functional demos. For all that material, we will ask interviewees to comment on its likely usefulness, its likely pitfalls or possible barriers to using it, and how we could improve it. We will also compile a wish list of app features and a list of things we should avoid.

Interviews will be audiotaped, and the tapes will be transcribed by a HIPAA-compliant service.

We have prior experience conducting this type of qualitative research with our participant population (Heinz et al., 2010).

3. Arm 1, Phase 2: Clinical trial with microrandomization

The following table shows the general timeline, which is explained in the sections that follow. *For analytical purposes, there are only two groups (JITAI vs. EMA control).* Procedurally, some participants will receive buprenorphine here at Archway (OBOT participants) and others will be treated elsewhere (TE participants). The recruitment of both OBOT and TE participants is not intended to bear directly on the science of the protocol; rather, it helps us enroll participants more quickly (our experience in the 020 protocol is that we enroll

an average of 4 OBOT participants and 4 TE participants every 30 days) and, as an additional advantage, may expand the population to which we can generalize our results (though we have not seen any appreciable demographic differences between OBOT and TE participants).

week	JITAI (OBOT)	EMA control (OBOT)	JITAI (TE: Treatment Elsewhere)	EMA control (TE: Treatment Elsewhere)
1	stabilize on bup; intro session (EMA + CBT/ACT); baseline questionnaires	stabilize on bup; intro session (EMA); baseline questionnaires	intro session (EMA + CBT/ACT); baseline questionnaires	intro session (EMA); baseline questionnaires
2				
3				
4				
5	JITAI – push 4x/day (first 16 nights will also include “Deep Dive” lessons/exercises on smartphone)			
6		EMA	JITAI – push 4x/day (first 16 nights will also include “Deep Dive” lessons/exercises on smartphone)	EMA
7				
8				
9				
10	JITAI – pull		JITAI - pull	
11	outcome assessment	outcome assessment	outcome assessment	outcome assessment
12				
13				
14	bup taper or transfer	bup taper or transfer		
15				
16				

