Participants in the formative-interview phase may reenroll for the randomized treatment phase. We want to give them access to the potential benefits of the intervention. When we analyze results, we will test whether the interviewed participants respond differently from newly enrolled participants, as might be expected from their having had input into the app design.

After signing informed consent, each participant will be randomly assigned to one of two groups: JITAI intervention or EMA only.

During the first two weeks of participation, each participant will have an in-person session for training appropriate to his or her study group. All participants will be shown how to use the smartphone to make entries. Participants randomized to the JITAI intervention will be introduced to some basic principles of CBT and ACT. We are forgoing extensive in-person training in the hope of demonstrating that our ambulatory intervention can be effective without that. Mindfulness and ACT, like CBT, can be learned through “unguided self-help” (that is, without in-person training) (Cavanagh et al., 2014). A mere 11 minutes of prerecorded audio instruction on mindfulness, delivered in a clinic, was superior to a relaxation control condition

in helping at-risk drinkers reduce their drinking over the next week (Kamboj et al., 2017). We will provide more support: during the initial in-person session, each participant will watch a video introduction to both CBT and ACT. The video will be approximately 20 minutes long, and will be recorded by a counselor who has experience delivering these kinds of interventions for addiction. We will use just one counselor to discuss both techniques to avoid any confounding by participant preference for one counselor over another.

Before and after the video, one of the investigators at our clinic will talk with the participant to address concerns and discuss any material that the participant found unclear. Investigators will also be available to answer participants' questions about CBT and ACT throughout their time in the study, either during clinic visits, or by phone or online.

The content of the video will be underscored and complemented by a series of lessons/exercises that participants will read at home on their smartphone, one per night, for the first 16 nights of the JITAI intervention. We describe the lessons/exercises (to be referred to as "Deep Dives") further down, after we describe the JITAI intervention.

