The enrollment ceiling is 35 outpatients (to collect evaluable data from 30) who meet these criteria: (1) Age 18-75; (2) physical dependence on opioids (by self-report; can include current agonist maintenance); (3) interest in receiving the types of treatment about which we will be conducting interviews (asked via “fact sheet” on the first day of in-person screening).

Phase 2: Clinical trial with microrandomization.

The enrollment ceiling is 150 outpatients (to collect evaluable data from 85, of whom 50 will be randomized to JITAI, and 35 to EMA control). Treatment may be provided by us in the form of office-based buprenorphine treatment (OBOT) or may be provided elsewhere (Treatment Elsewhere, TE). Participants must meet these criteria:

OBOT participants: (1) Age 18-75; (2) physical dependence on opioids (by positive urine and/or frank opioid withdrawal); (3) interest in receiving the types of treatment we are testing (asked via “fact sheet” on the first day of in-person screening).

Treatment Elsewhere (TE) participants: (1) Age 18-75; (2) receiving methadone or buprenorphine treatment for opioid dependence from a qualified provider in the community; (3) interest in receiving the types of treatment we are testing (asked via “fact sheet” on the first day of in-person screening).

2. Exclusion criteria

Phase 1: Formative interviews. (1) cognitive impairment severe enough to preclude informed consent or valid interview responses (History & Physical and Evaluation to Sign Consent).

Phase 2: Clinical trial with microrandomization.

OBOT and TE participants: (1) History of any DSM-5 psychotic disorder; history of bipolar disorder; current Major Depressive Disorder (MINI structured interview); (2) unresolved symptoms of PTSD that, in the investigators’ view, would make it risky for the participant to undertake mindfulness exercises (e.g., observing all one’s current negative thoughts and emotions) in an unsupervised setting (MINI structured interview); (3) current dependence on alcohol or sedative-hypnotic, e.g. benzodiazepine (by DSM-5 criteria in MINI structured interview); (4) cognitive impairment severe enough to preclude informed consent or

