of days in each study phase, and thus in the general timeline of the study. Further, due to the lack of a medication dose ceiling in this protocol and the desire to maximize taper success and participant comfort, the study physician may: (1) hold the medication taper at a given dose, which may add up to 2 weeks to this phase; (2) alter the taper decrement by requesting a specified dose decrease (e.g., decrease buprenorphine by 2mg x 3 days) which will slow the rate of taper and may add up to 2 weeks to this phase; and (3) may prescribe medications for the symptomatic relief of withdrawal signs and symptoms. These medications may include but are not limited to: ibuprofen, acetaminophen, hydroxyzine, dicyclomine, magnesium hydroxide, loperamide, and trimethobenzamide. These clinically indicated steps may add up to 2 weeks to the medication taper, which would result in a maximum total of a 7-week taper. These decisions will be made by the study physician as medically indicated based on withdrawal signs and symptoms and cravings.

Compliance with EMA and JITAI

If an OBOT participant misses 4 appointments, he or she may be discharged with a 21-day taper. Given their shorter length of participation, TE participants can be discharged if they miss 3 visits.

Participants must complete entries for at least 82% of all random prompts. This will be assessed weekly. Participants will receive approximately 28 prompts per week. Missing five entries per week would correspond to a compliance rate of 82.1%. If a participant falls below the 82% completion rate one week, the participant will be reminded of the requirement; if the participant remains below 82% during the next week, the participant will be eligible to be discharged. In the JITAI group, each pair of “pre” and “post” assessments will be counted as part of the same entry; both have to be completed for the entry to be considered completed.

Each participant will have a brief weekly meeting with a study-team member to receive a small payment (discussed in Section S, Compensation) for compliance with EMA requirements, or to be warned that he or she needs to comply with EMA requirements.

Participants in the JITAI group must read/do all 16 “Deep Dive” lessons/exercises within the first 21 nights of the JITAI intervention. Failure to do so will result in discharge.

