For each participant in the JITAI group, we will use multilevel models with person-specific slopes to quantify the relative overall effectiveness of CBT vs. ACT messages during the “push” weeks, in terms of proximal changes craving, self-efficacy, and/or mood. We will then calculate the participant’s relative overall preference for CBT vs. ACT content during the “pull” week. These can be straightforwardly shown in a scatterplot with an accompanying bivariate correlation coefficient.

3. Criteria for statistical significance

The criterion for statistical significance will be set at $p \leq 0.05$, two-tailed. For hypothesized effects that do not reach statistical significance, we will calculate Bayes factors (Dienes, 2014), which help determine whether “nonsignificant” findings favor the null or the alternative hypothesis or whether they should be considered inconclusive.

J. Required sample size

For the formative-interview phase, we anticipate that 30 interviewees will be sufficient to give us feedback on our prototype materials and app interface. We may revisit this if we find that responses are highly variable across interviewees. We expect that most people who agree to be interviewed will provide usable information, so we are setting out enrollment ceiling at 35.

For the microrandomized trial, which is longer and more demanding, we expect a higher rate of dropout. We will enroll up to 150 participants to reach a target of 85 (50 JITAI, 35 EMA control) who complete the week-eleven outcome assessment. The calculations that led us to that total are as follows.

For hypothesis 1 (the proximal main effect of messaging in the microrandomized trial), we used a power-and-sample-size calculator <<https://pengliao.shinyapps.io/mrt-calculator/>> developed specifically for microrandomized studies (Liao et al., 2016). This calculation applies specifically to the JITAI group, not the EMA control group. As Liao et al. (2016) point out, there is very little precedent for determining what a proximal effect size should look like, but small studies with microrandomized designs can often detect seemingly small effects, on the order of $d = .15$. We decided that the most important consideration was to set our beta level high (.90, rather than the conventional .80), and we started by entering the following assumptions:

Days of study: 56 [eight weeks of “push” intervention].

Number of decision time points per day: 4.

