A meta-analysis we cited earlier suggested effect sizes on the order of .57 for a smartphone intervention versus standard treatment (Lindhiem et al., 2015). For some of the comparisons of interest here, such as expansion of the repertoire of coping strategies, group differences are likely to be even larger, because our control condition will not include any instruction relevant to them. With evaluable data from 50 participants in the JITAI group and 35 in the EMA control group, we will have power of .90 (in two-tailed tests) to detect a group difference of $d = .70$ or larger in any overall outcome. At the more conventional beta of .80 (in two-tailed tests), we will have power to detect a d of .60 or larger.

K. Plans for enrollment at multiple sites

Not applicable.

L. Human-subjects protection plan

1. Rationale for subject selection based on gender/ethnic/race categories at risk

Participant selection will be equitable, without regard to nationality, sex, race, religion, or creed. The anticipated racial/ethnic and sex distribution will reflect that of the local community and drug-using population.

The use of mindfulness interventions in the US might seem, on its face, like a trend that would appeal primarily to a culturally or economically privileged few. In fact, however, focus-group data from Washington, DC, show that low-SES African-American clinic attendees find mindfulness exercises helpful and empowering (Spears et al., 2017). Lessons learned from those prior focus groups, and from the formative interviews we do, will help shape our interventions.

2. Recruitment plan

Recruiting

Standard recruitment efforts employed by MMG will be used for this nonresidential treatment study (See NIDA/IRP Medical Policy and Procedure Manual). MMG advertises extensively in a variety of newspapers that are read by both sexes and all ethnicities. Special outreach efforts are made toward women and minorities.

Ads will be submitted to the IRB for approval before they are used.

Our experience with OBOT and TE patients in the 020 protocol is that we enroll each type at a rate of about 4 every 30 days. If that rate (8 enrollees every 30 days) is maintained, we should reach our enrollment target of 175 in just under 660 days, with roughly equal numbers of OBOT and TE participants.

Screening methods

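### OBOT/TE status, known before randomization and plausibly prognostic for urine results and retention, appears neither in the described allocation nor in any hypothesis 3 analysis

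*Combined protocol and SAP*

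**What the plan says.** Section E.3 of the combined protocol and SAP describes assignment in one sentence: "After signing informed consent, each participant will be randomly assigned to one of two groups: JITAI intervention or EMA only". Section J adds that allocation is deliberately unequal. Neither section mentions stratification, blocking or minimization. The Précis treats the place of treatment as procedural and outside the design, and Section E.3 states: "For analytical purposes, there are only two groups (JITAI vs. EMA control".

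The two strata enter by different routes (Section F.1). OBOT participants qualify by "physical dependence on opioids (by positive urine and/or frank opioid withdrawal"; TE participants qualify by "receiving methadone or buprenorphine treatment for opioid dependence from a qualified provider in the community". OBOT participants are stabilized on buprenorphine during weeks 1-2 (Sections E.3 and G). Under Section G, "TE participants can be discharged if they miss 3 visits", whereas the OBOT limit is 4. Only TE participants are paid per visit (Section S).

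For hypothesis 3 (Section I.2), the ANCOVAs of FIT-60, DTCQ and COPE contain group and the week-2 score. The generalized linear mixed model (GLMM) for thrice-weekly opioid urine and the comparison of treatment success (completing week 11 with an opioid-negative test that week) have no baseline covariate named.

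**The concern.** OBOT/TE status is fixed by the entry criteria, and TE treatment is confirmed at screening (Section L.2), so it is available before assignment. It plausibly matters for two things: opioid-positive urine, because one stratum enters using opioids or in withdrawal while the other is already on agonist treatment; and retention, because the missed-visit limits and visit payments differ. The urine model covers the whole study, including the OBOT stabilization weeks, and success requires both retention and a negative test.

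The only similarity that the protocol reports between the strata is demographic (Section E.3). It says nothing about urine results, dropout or self-efficacy. If the arms happen to differ in OBOT share, part of any JITAI-versus-EMA difference in urine or success would reflect stratum mix, and no planned term would remove it. Even with balanced arms, stratum variation stays in the residual. A covariate added after an imbalance has been seen would look data-driven.

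**Working it through.** **The plan's own figure.** Section I.3: "The criterion for statistical significance will be set at $p \leq 0.05$, two-tailed". Section J: "With evaluable data from 50 participants in the JITAI group and 35 in the EMA control group, we will have power of .90" "to detect a group difference of $d = .70$ or larger in any overall outcome". It also states power .80 at d = .60.
- Standard error in SD units: sqrt(1/50 + 1/35) = .2204.
- d = .70: .70/.2204 - 1.96 = 1.216, power .888 (noncentral t: .881). This agrees with .90 after rounding.
- d = .60: .60/.2204 - 1.96 = .762, power .777 (noncentral t: .768), slightly under the stated .80.

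**Inputs for imbalance.** OBOT share is about one half (Section L.2 expects roughly equal numbers). The ceiling is 150 randomized for 85 evaluable, 50 JITAI and 35 EMA (Section J). Applying 50:35 to 150 gives 150 x 50/85 = 88.2, so about 88/62; this assumes that allocation follows the evaluable ratio.

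**Which count applies.** The GLMM is meant to keep dropouts' data, and success is a proportion of the participants in each group, so a dropout counts as a failure. Both use randomized participants, up to 150. The ANCOVAs use only those who reach week 11.

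**Chance imbalance in OBOT share.** SD = sqrt(.25 x (1/n1 + 1/n2)), with two-sided normal tails and exact hypergeometric values in brackets:

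| Set | SD | P(15 points or more) | P(20 points or more) |
|---|---|---|---|
| Randomized, 88/62 | .083 | .070 (.068) | .016 (.013) |
| Completers, 50/35 | .110 | .173 (.188) | .070 (.078) |

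If the study stops below 150 because the completer target is met, the first row moves toward the second.

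**Shift in the group difference** = imbalance x difference between strata. The documents give no outcome figure by stratum, so a range of 20 to 40 points in opioid-positive rate is assumed.
- One SD: .083 x .20 = .017 to .083 x .40 = .033, or 1.7 to 3.3 points.
- 15 points: .15 x .20 = .03 to .15 x .40 = .06, or 3 to 6 points.

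For scale, the standard error of a simple difference in success proportions near 50% (assumed) at 88/62 is sqrt(.25 x (1/88 + 1/62)) = 8.3 points. The 15-point case is therefore 3/8.3 = 0.36 to 6/8.3 = 0.72 standard errors.

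**Precision.** Let the strata differ by D within-stratum SDs beyond what the week-2 score explains (assumed). With half in each stratum, total variance is 1 + D²/4, and adjustment multiplies d by sqrt(1 + D²/4). At 50/35 and d = .60, noncentral-t power goes from .768 to .772 (D = 0.2), .792 (D = 0.5) or .853 (D = 1.0).

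**The case against.** The strongest reply is that this is a disclosed choice with limited reach. The proximal and strategy-situation-fit outcomes are within-person comparisons in the JITAI group, so stratum imbalance between arms does not touch them. The primary distal outcomes, self-efficacy and coping flexibility, are already adjusted for the week-2 score. Opioid urine is secondary, and Section I.2 says that cessation of use is not the main outcome. TE entry does not require an opioid-negative urine, and OBOT participants are stabilized before the smartphone phase. All of this stands and narrows the point. It does not remove it for urine and success, where no baseline covariate is named. The week-2 score absorbs only the part of a stratum difference that shows at baseline.

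A reader might infer more than the documents support:
- That OBOT/TE is a strong prognostic factor. No outcome data by stratum are given; the entry criteria support plausible and no more.
- That the trial is biased or its error rate inflated. Randomization protects both unconditionally.
- That the imbalance probabilities of .17 and .07 apply to urine and success. They fit the 85 completers in the ANCOVAs.
- That the plan rejects stratification or forbids a covariate. Section E.3 gives no method of sequence generation, and the two-groups sentence can be read as defining the treatment contrast. The gap is silence on allocation and the absence of a named term.

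**Conclusion.** The point holds as a modest, nearly free improvement. A plausible prognostic factor, known before assignment, is used neither in the described allocation nor in any hypothesis 3 analysis. The exposure is conditional bias and lost precision, mainly in the urine GLMM and the success comparison. A 15-point imbalance there has a chance of about .07 and would move the difference by 3 to 6 points; a typical one-SD imbalance would move it by 1.7 to 3.3. In the ANCOVAs imbalance is more likely, but the week-2 score already removes part of its effect.

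These sizes rest on a half-OBOT sample, about 88/62 randomized, and an assumed 20-to-40-point difference between strata. A smaller true difference shrinks the shifts in proportion, and with no difference there is no shift and almost no cost to adjusting.

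**What to change.** 1. Prespecify OBOT/TE as a fixed covariate in the urine GLMM and in the treatment-success comparison, and add it to the FIT-60, DTCQ and COPE ANCOVAs alongside the week-2 score. State that the two-group treatment contrast is unchanged.
2. State how the allocation sequence is generated, and stratify the 50:35 allocation by OBOT/TE. If enrollment has begun, stratify the remaining participants.

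The covariate is the main remedy. Stratified allocation balances the arms at entry, but it cannot stop stratum-dependent dropout, which the different missed-visit limits could produce, from changing the mix among completers.

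The cost is a second allocation list and one degree of freedom. Eligibility, sample size, visits and data collection stay as they are. The covariate should be written into the plan before outcome data are compared by group.

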Evening “Deep Dives” into ACT and CBT. For each of the first 16 evenings, the app will display a more in-depth lesson/exercise for participants in the JITAI group. The display time will have been selected by the participant during the issuing of the smartphone. The participant can “snooze” the “Deep Dive” (reschedule it for later in the evening), but has to read/do it on the scheduled evening. The “Deep Dives” (shown in Appendix B), which should each take approximately 5-15 minutes, will underscore and complement the general teaching on the introductory video. The intention is to provide skill training and philosophical context that will increase the value of the brief daily ACT and CBT messages. “Deep Dives” will alternate nightly between ACT and CBT and will be presented in the same order for all participants. The presentation of lessons in standardized sequence is typical for mobile interventions that include instructional modules. By giving the Deep Dives in the same order for everyone, we can present them more coherently. We think of the 16-night Deep Dive period almost as a psychological analog of a buprenorphine-induction period: at the end of it, every participant will have been titrated up to our targeted “dosage” of concept teaching and skill teaching.

We drew the material for the CBT “Deep Dives” from publicly available sources (such as the NIDA online “toolbox”); we drew the material for the ACT “Deep Dives” from publicly available sources and from a workbook by [name] (Hayes & Smith, 2005).

We will encourage participants to read/do the “Deep Dives” as scheduled, and we will discharge participants who have not done all 16 within the first 21 nights. That is, we will permit (but not encourage) up to five missed nights, and when a night is missed, the “Deep Dives” will resume with the missed material, adding one night to the total length of presentation.

The “Pull” Period. Participants in the JITAI group who complete the 7-week push period will immediately continue to the 1-week pull period. The pull period will be a superimposition of pull upon of push: push messages and assessments will continue as before, mostly because we want to continue collecting full daily data on every participant. But participants will also be able to initiate (pull) the “Deep Dives” they have already read/done, or view messages as

needed. Each time they do so, they will have their choice of: (1) any specific ACT Deep Dive, (2) any specific CBT Deep Dive, (3) an ACT message to be chosen at random by the app, or (4) a CBT message to be chosen at random by the app. Thus, we will be able to assess preferences for both the philosophical approach and the format.

If it is technically feasible, we will give participants access to one additional pull intervention: a “get me out of this” tool, intended to help them extricate themselves from social situations that lead to lapses. When we have interviewed our participants in prior studies to generate personalized craving-induction scripts (Jobes et al., 2015), we have found that one of the more frequent lapse scenarios is a chance encounter with, or phone call from, a friend who casually suggests getting high. We will try to implement a feature that, when surreptitiously pulled by the user, can simulate the arrival of an urgent message (for extrication from in-person encounters) or generate avoidance strategies that the user might not immediately think of (for extrication from phone/online encounters).

EMA data will be transferred wirelessly from participants’ phones to servers located at the NIDA BRC under a secure communications system developed by the NIDA Biomedical Informatics Section (BIS). Transfers will be scheduled to occur automatically at least twice a day. Participants will not have to visit the laboratory for these data transfers. If the remote transfers fail, we can manually initiate a wireless transfer when participants make their regularly scheduled laboratory visits. If that fails, we will swap out the participant’s phone so BIS can try to recover the data.

During week 11, all participants will be assessed for overall treatment outcome. This will include second administrations of some of the baseline questionnaires (the FIT-60 mindfulness measure, the DTCQ measure of self-efficacy to cope with drug temptations, the MCQ for delay discounting, the TSPQ-21 for Twelve-Step involvement, and the COPE measure of breadth of coping styles). Most other aspects of treatment outcome will be operationalized during data analysis as summary measures from EMA and urine data collected over the course of treatment.

F. Inclusion and exclusion criteria

1. Inclusion criteria

Phase 1: Formative interviews.

The enrollment ceiling is 35 outpatients (to collect evaluable data from 30) who meet these criteria: (1) Age 18-75; (2) physical dependence on opioids (by self-report; can include current agonist maintenance); (3) interest in receiving the types of treatment about which we will be conducting interviews (asked via “fact sheet” on the first day of in-person screening).

Phase 2: Clinical trial with microrandomization.

The enrollment ceiling is 150 outpatients (to collect evaluable data from 85, of whom 50 will be randomized to JITAI, and 35 to EMA control). Treatment may be provided by us in the form of office-based buprenorphine treatment (OBOT) or may be provided elsewhere (Treatment Elsewhere, TE). Participants must meet these criteria:

OBOT participants: (1) Age 18-75; (2) physical dependence on opioids (by positive urine and/or frank opioid withdrawal); (3) interest in receiving the types of treatment we are testing (asked via “fact sheet” on the first day of in-person screening).

Treatment Elsewhere (TE) participants: (1) Age 18-75; (2) receiving methadone or buprenorphine treatment for opioid dependence from a qualified provider in the community; (3) interest in receiving the types of treatment we are testing (asked via “fact sheet” on the first day of in-person screening).

2. Exclusion criteria

Phase 1: Formative interviews. (1) cognitive impairment severe enough to preclude informed consent or valid interview responses (History & Physical and Evaluation to Sign Consent).

Phase 2: Clinical trial with microrandomization.

OBOT and TE participants: (1) History of any DSM-5 psychotic disorder; history of bipolar disorder; current Major Depressive Disorder (MINI structured interview); (2) unresolved symptoms of PTSD that, in the investigators’ view, would make it risky for the participant to undertake mindfulness exercises (e.g., observing all one’s current negative thoughts and emotions) in an unsupervised setting (MINI structured interview); (3) current dependence on alcohol or sedative-hypnotic, e.g. benzodiazepine (by DSM-5 criteria in MINI structured interview); (4) cognitive impairment severe enough to preclude informed consent or

valid self-report (History & Physical and Evaluation to Sign Consent); (5) Any condition that interferes with urine collection (by self-report, medical records, or physical exam); (6) medical illness (e.g., cirrhosis, nephritic syndrome, thyroid disease, ischemic heart disease, epilepsy, adrenal insufficiency, etc., by self-report, medical records, or physical exam) or medications that, in the view of the investigators, would compromise participation in research.

The exclusion of people with current unresolved PTSD symptoms will apply regardless of whether full criteria for a diagnosis have ever been met. Standard screening on the MINI structured interview will flag those instances, which will be followed up by further questioning from MMG counselors and, as appropriate, consultation between MMG staff and the MAI and/or the Principal Investigator. We will give particular consideration to applicants' stated feelings about whether the JITAI app might be risky for them, but we intend to err on the side of caution.

The exclusion for alcohol or sedative-hypnotic dependence reflects the medical complications of tapering from those substances. We will not automatically exclude applicants who use or have DSM diagnoses involving other substances (such as cannabis). The JITAI intervention, though focused on opioids and cocaine, is likely to be relevant to most drugs of abuse.

G. Clinical and laboratory methods

OBOT participants: We will provide office-based buprenorphine treatment. Participants will visit the clinic at least 3 times a week. If needed, participants can be asked to come in for visits up to 5 times in the first 7 days to help with induction or to establish a pattern of attendance. Participants will receive buprenorphine doses delivered in the clinic, with take-home doses given for the rest of the week. Urine and breath samples will be collected at each study visit under direct observation by trained staff (prior to dosing) during weeks 1-11 and during the optional buprenorphine taper (weeks 12-16). Urine will be tested on site, by dipstick, for drug metabolites; the panel used at Archway currently includes tests for amphetamines, benzodiazepines, buprenorphine, cannabinoids, cocaine, MDMA, methadone, morphine (heroin metabolite), and oxycodone. An aliquot of each urine specimen will be immediately labeled and frozen at -30°C in case additional analyses are needed (e.g., if a result is inconclusive). The drug-test results are used as research data (reflecting one element of treatment response) and to help the Archway counselor assess participants' ongoing treatment needs.

Breath will be tested for alcohol using an Alco-Sensor III (Intoximeter, Inc.; St. Louis, MO). The breath results are used as research data and to help the counselor assess needs; they are also used by the Archway nurses to help determine when a buprenorphine dose should be withheld for safety.

Additionally, participants will self-report recent drug use using a standardized questionnaire on these days.

These procedures will continue through the entirety of the study.

Treatment Elsewhere (TE) participants: Participants will visit the clinic 3 days per week. As these participants are receiving their treatment outside of the NIDA IRP, staff will not be monitoring or dosing methadone or buprenorphine in these participants. Urine testing, breath testing, and self-report will be the same as for OBOT participants, except that an alcohol-positive breath reading cannot affect dosing decisions.

Research vs. Clinical care

We deliver buprenorphine treatment in a manner consistent with standard clinical care. It is necessary to deliver these forms of treatment within our research clinic because the required level of data collection would not be practical outside of treatment delivery or in a community clinic. Urine drug testing is a standard in clinical care; however, the frequency of collection (three times weekly) is greater than in most community treatment programs and is part of the research methodology in this protocol. All other measures are considered part of research.

The weekly counseling session will be delivered by a master's-level counselor at Archway. The focus will be on case management, meaning practical matters such as job searches, housing stability, medical/dental/insurance issues, and GEDs. Participants can also raise emotional issues as needed.

The timeline below is in chronological order (including duration of study, number of visits, and time commitment for participants).

Day 1: Consent and beginning of treatment

Participants will visit the clinic three days a week. Participants will be allowed to reschedule an appointment twice during the study if they miss an appointment or need to come in on an earlier day.

- Participants' buprenorphine will be stabilized during weeks 1 and 2 using flexible dosing under the supervision of the MAI.

Week 1-2: During the first two weeks, participants will undergo training appropriate to their randomized group; for the EMA control group, this will consist only of training on how to do EMA, not video material on CBT or ACT. Participants will also fill out baseline questionnaires, usually on a separate day.

End of Week 2

JITAI/EMA begins. Each participant will be issued a smartphone and reminded how to use it.

Week 11: Discontinuation of JITAI/EMA; outcome assessment.

- JITAI/EMA will end after week 10. Participants will be compensated for return of the smartphone.
- All participants will be readministered some of the baseline questionnaires (as specified above in the questionnaire descriptions) to assess changes in mindfulness, self-efficacy, need for closure, and coping styles.

Weeks 12-16: Optional buprenorphine taper for OBOT participants.

- Participants will be encouraged to and assisted in transferring to a community treatment program for continuation of care. Participants who do not wish to transfer to continued treatment in the community will be tapered from buprenorphine at Archway over 5 weeks with an optional additional 2 weeks if needed to secure transfer or to treat opioid withdrawal symptoms and minimize chances of relapse. At any time during the taper, participants can choose to transfer to another program.
- Transfer of care/continuity of care – Throughout the study, counselors will be engaged with participants about plans for care/treatment/counseling following discharge from the study (i.e., aftercare). Aftercare, of some kind, is always recommended. For those participants who continue to use illicit drugs or who relapse to use, community-based methadone and/or buprenorphine programs are recommended. Participants will be given a list of treatment programs and must initiate the contact. Archway staff will supply the transfer summary and help to coordinate a transfer date. Depending on the participants' input and status, a drug-free counseling center or Narcotics Anonymous (NA) may also be recommended. Throughout their time at Archway, participants have access to lists of alternative and aftercare programs, private MDs as well as applications for financial support, subsidized healthcare, health insurance, job and housing opportunities, etc.
- Due to clinical considerations, taper procedures can occasionally alter the total number

of days in each study phase, and thus in the general timeline of the study. Further, due to the lack of a medication dose ceiling in this protocol and the desire to maximize taper success and participant comfort, the study physician may: (1) hold the medication taper at a given dose, which may add up to 2 weeks to this phase; (2) alter the taper decrement by requesting a specified dose decrease (e.g., decrease buprenorphine by 2mg x 3 days) which will slow the rate of taper and may add up to 2 weeks to this phase; and (3) may prescribe medications for the symptomatic relief of withdrawal signs and symptoms. These medications may include but are not limited to: ibuprofen, acetaminophen, hydroxyzine, dicyclomine, magnesium hydroxide, loperamide, and trimethobenzamide. These clinically indicated steps may add up to 2 weeks to the medication taper, which would result in a maximum total of a 7-week taper. These decisions will be made by the study physician as medically indicated based on withdrawal signs and symptoms and cravings.

Compliance with EMA and JITAI

If an OBOT participant misses 4 appointments, he or she may be discharged with a 21-day taper. Given their shorter length of participation, TE participants can be discharged if they miss 3 visits.

Participants must complete entries for at least 82% of all random prompts. This will be assessed weekly. Participants will receive approximately 28 prompts per week. Missing five entries per week would correspond to a compliance rate of 82.1%. If a participant falls below the 82% completion rate one week, the participant will be reminded of the requirement; if the participant remains below 82% during the next week, the participant will be eligible to be discharged. In the JITAI group, each pair of “pre” and “post” assessments will be counted as part of the same entry; both have to be completed for the entry to be considered completed.

Each participant will have a brief weekly meeting with a study-team member to receive a small payment (discussed in Section S, Compensation) for compliance with EMA requirements, or to be warned that he or she needs to comply with EMA requirements.

Participants in the JITAI group must read/do all 16 “Deep Dive” lessons/exercises within the first 21 nights of the JITAI intervention. Failure to do so will result in discharge.

